### 6.7.2 Statistical Analyses of Secondary Endpoints

Statistical Analyses of Primary BoE (Day 56 only), Secondary BoE, BoPH, Physiologic Endpoints, and Subjective Measure Endpoints (*my*bluTM Products Versus the Continue-smoking Arm)

An approach similar to that used for the primary endpoints will be used to make Day 28 and Day 56, as applicable, change-from-baseline comparisons between the *my*bluTM products and the continue-smoking arm for the applicable primary and secondary BoE, BoPH, physiologic endpoints, and subjective measure endpoints as described in the SAP. For the Day 56 analysis, the initial *my*bluTM flavor Product assignments for each subject will be maintained within the statistical model and a separate sensitivity analysis will be performed for subjects that do not switch flavors at Day 29.

The ITT population will be used for these analyses.

# Statistical Analyses of Primary BoE (Day 56 only) and Secondary BoE (Within *my*bluTM Products)

Comparisons of the primary and secondary BoE change-from-baseline values at each time point within the mybluTM products will also be made using a linear mixed model ANOVA.

# Statistical Analyses of Pharmacokinetics (*my*bluTM Products Versus the Continuesmoking arm or JUUL arm)

A linear mixed model ANOVA will be performed on the log-transformed nicotine PK parameters AUC and Cmax from each product use session (PK population). The model will include product arm as a fixed effect. Geometric LSMs will be provided for the PK parameters of Cmax and AUC by product arm. Geometric LSM ratio, 95% confidence intervals of geometric LSM ratio, and p-values will be provided for the product arm comparisons for Cmax and AUC. The comparisons of interest will include each of the *my*bluTM product arms compared to continue-smoking arm or JUUL arm. The above statistical analyses will be performed using the following SAS codes.

```
Proc MIXED data=<>;
Class subject arm;
Model LN_dependent variable = arm/DDFM=KR;
LSMeans arm/pdiff CL alpha=0.05;
Run;
```

Non-parametric analysis (Wilcoxon Rank Sum test) will be performed for the comparisons of  $T_{max}$  between test and reference products.

Similar methods will be used to compare the urge to smoke parameters.

#### 7. SAFETY

All case report form (CRF) data will be listed by subject and chronologically by assessment time points. This will include rechecks, unscheduled assessments, and early termination.

Applicable continuous variables will be summarized using n, arithmetic mean, SD, minimum, median, and maximum.

The level of precision will be presented as follows: minimum/maximum in the same precision as in the database, mean/median in one more precision level than minimum/maximum, SD in one more precision level than mean/median, and n will be presented as an integer.

Where individual data points are missing because of dropouts or other reasons, the data will be summarized based on reduced denominators.

# 7.1 Subject Discontinuation

Subjects will be summarized by number of subjects enrolled, randomized, completed, and discontinued the study with discontinuation reasons by randomized product arm and overall.

# 7.2 Demographics

Descriptive statistics will be calculated for continuous variables (age, weight, height, and body mass index) by randomized product arm and overall.

Frequency counts will be provided for categorical variables (race, ethnicity, and sex, and other characteristics) for each randomized product arm and overall.

#### 7.3 Smoking History

Descriptive statistics will be calculated for continuous variables (cigarettes smoked per day [CPD] and number of years smoked) by randomized product arm and overall.

Frequency counts will be provided for subject's usual brand for each randomized product arm and overall.

#### 7.4 Adverse Events

All adverse events (AEs) occurring during this clinical trial will be coded using the Medical Dictionary for Regulatory Activities (MedDRA®), Version 21.0.

All AEs captured in the database will be listed in by-subject data listings including verbatim term, coded term, product, severity, relationship to study product, and action; however, only product use-emergent AEs (PUEAEs) will be summarized.

A PUEAE is defined as an AE that is starting or worsening at the time of or after the first randomized study product use. Each PUEAE will be attributed to a study product based on the onset date and time of the AE.

If the onset time of an AE is missing and the onset date is the same as the first study product use date, then the AE will be considered product use emergent in the study product. If onset time of an AE is missing and the onset date does not fall on a study product use date, then the AE will be considered product use emergent for the last study product administered. If the onset date of an AE is missing, then the AE will be considered product use emergent, unless the onset date is known to have occurred within or between specific product use days.

PUEAEs will be tabulated by System Organ Class (SOC) and Preferred Term. Summary tables will include number of subjects reporting the AE and as percent of number of subjects used study product by product. The number of AEs will be tabulated in a similar manner. Tables which tabulate the number of PUEAEs by severity and relationship to study product will also be included.

In addition, adverse events occurred during baseline period on Day -2 and day -1 will be summarized separately.

Serious adverse events (SAEs), if present, will also be listed. Applicable narratives will be included in the CSR.

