5.2 Study Product Accountability

The staff at each site will coordinate shipping of the mybluTM products from the Sponsor (or a distribution vendor). JUUL[®] products will be obtained from commercial sources. The clinic staff will document the date products were received and recorded in the inventory records, the content of all shipments received, the total number of products dispensed during the study, and the total number of products remaining at the end of clinical conduct.

Appropriate documentation of the receipt and return of products supplied by subjects must also be kept. Subjects will be required to provide enough unopened packs of their usual brand cigarettes for use during the test visits (calculated as cigarettes smoked per day times the number of days in confinement, rounded up to the next pack, plus two packs). Cigarette packages that have been opened prior to check-in for the test visit are not to be accepted for use in the clinic and subjects will be reminded of this requirement during the reminder phone call. If a subject presents to a test visit with only opened packages, presents to the clinic with an insufficient supply based on reported CPD, or if the subject runs out of cigarettes during the confinement period, the subject or site should purchase a sufficient number of packages for use and this information will be documented appropriately. Unused cigarettes will be returned to the subjects in the continue-smoking arm at discharge for each confinement test visit and to the *my*bluTM and JUUL[®] arms at discharge from the study.

For each subject, dispensing records for in-clinic use must include the date and time study products were dispensed and returned, or in the case of the PK sessions, the start and stop time of the session. If a subject mistakenly disposes of a product, a reasonable effort should be made to retrieve the product. If retrieval is not possible, the approximate time that use of the product was finished and a description of the occurrence should be noted in the source documents. The subject will be advised that further disposal may result in dismissal from the study. Reconciliation of the dispensed and returned products should be completed to ensure adequate accountability of the products. If a daily allotment of products is transferred to the

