The PK sub-study will assess nicotine uptake and urge to smoke from the mybluTM products relative to combustible cigarettes and an e-cigarette comparator (JUUL®). A subset of up to 20 subjects assigned to each of the mybluTM e-liquids, 20 subjects from the continue-smoking arm, and all 20 subjects in the JUUL® arm will participate. Subjects in the JUUL® arm will begin using the product after check-in (Day -2) for Test Visit 1 and will continue to use the product through discharge on Day 1 from the study following the PK assessment (subjects in the JUUL® arm will only participate in the PK sub-study). PK assessments will be preceded by a minimum 10-hour abstention from product use and will take place on Day 1 for the JUUL® and continue-smoking arms, and on Day 5 for the *my*bluTM arm. Product use for the PK assessments will consist of two sessions: 1) a fixed/controlled puffing session in the morning consisting of 10 puffs taken at 30 second intervals, with puffs 3 seconds in duration, and 2) an *ad libitum* use session beginning 6 hours after the start of the morning session and consisting of unlimited use of the e-cigarette product for 5 minutes or one cigarette, with no limits on puff duration or inter-puff interval. No product use of any kind will be allowed between the sessions. E-cigarette pods used for each session will be weighed before and after use to measure the amount of e-liquid used.

All product use during confinement will be documented by the clinic staff. Subjects in the *my*bluTM and continue-smoking arms will be required to self-report product use from Day 3 through discharge from the study.

Exhaled CO and urine cotinine measurements will be used to confirm smoking/nicotine use status prior to Day 1 and to assess subject compliance with product assignment requirements thereafter.

The clinic staff will contact all subjects via a telephone call approximately 14 days after discharge from the study (either as scheduled or after early termination) for reporting of AEs and use of concomitant medications.

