Screening of subjects will occur within 28 days prior to prior to check-in (Day -2) for Test Visit 1. Screening safety evaluations will include a physical examination, vital signs, ECG, clinical laboratory tests (clinical chemistry, hematology, urinalysis, and serology), lung function, urine drug tests, urine cotinine tests, and alcohol breath tests, FSH tests (post-menopausal females) and serum and urine pregnancy tests (females only).

On-study safety evaluations will include a symptom-driven physical examinations, vital signs, ECG, clinical laboratory tests (clinical chemistry, hematology, and urinalysis), lung function, and urine pregnancy tests (females only).

AEs spontaneously reported by the subjects or observed by the Investigator or other study personnel will be documented and monitored from the time of first product use after successful completion of the check-in (Day -2) events for Test Visit 1 through the end of the Follow-up Period. Any prior and concomitant medications taken from 30 days prior to Screening through the Follow-up Period will also be recorded.

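### SAP 7.4 sets no end to product attribution, so adverse events arising after e-cigarette supply has stopped fall into the last product's column, to a very unequal extent by arm

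*SAP*

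**What the plan says.** SAP 7.4 defines the events to be tabulated: "A PUEAE is defined as an AE that is starting or worsening at the time of or after the first randomized study product use". It gives a start and no end. It then requires that "Each PUEAE will be attributed to a study product based on the onset date and time of the AE". The only rule for an onset away from a product-use date covers AEs whose onset time is missing, for which "the AE will be considered product use emergent for the last study product administered".

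Collection runs well past product use. SAP section 3 has AEs monitored from first product use after the check-in "events for Test Visit 1 through the end of the Follow-up Period", with a call "approximately 14 days after discharge from the study (either as scheduled or after early termination) for reporting of AEs". Protocol 6.1.4 sets that call at 14 ± 2 days.

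At discharge the arms diverge:
- **E-cigarettes.** Under Protocol 5.4.2 only myblu is dispensed for ambulatory use, and pods come back at each later Test Visit. Table 2 shows no myblu dispensing after Test Visit 4. Protocol 5.6 has leftover myblu and JUUL items returned or destroyed.
- **Own cigarettes.** Protocol 5.2: "Unused cigarettes will be returned to the subjects in the continue-smoking arm at discharge for each confinement test visit and to the" myblu and JUUL arms when they leave the study.
- **Continue-smoking.** Under Protocol 5.1.2 these subjects bring their own product throughout, so nothing changes for them at discharge.

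The shells for Tables 14.3.1.1 to 14.3.1.3 have places for Product Trial, Products A to F and Overall. None is for follow-up.

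**The concern.** A follow-up AE in a myblu or JUUL subject qualifies as product-use emergent, must be given a product, and has only the last study product's column to go to. It is then counted as an e-cigarette AE although study supply has stopped and the subject's own cigarettes have been handed back. The continue-smoking column has no such change of product.

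At stake is what the Product A to F columns mean. The safety objective concerns a 56-day use period, and readers will take each column as the experience on that product. The SAP already sets aside time that does not represent the assigned product: the Product Trial column is left out of Overall, and AEs on Days -2 and -1 are summarized separately. Follow-up is the period still mixed in. Dividing by days over the same open window would not cure this, because the off-supply days would sit in both numerator and denominator.

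**Working it through.** **Inputs**
- JUUL use: Days -2, -1 and 1, with no Day 0, so 3 calendar days (SAP section 3; Protocol Table 3).
- Myblu use: assigned liquid from Day 3 to discharge on Day 57, 57 − 3 + 1 = 55 days (SAP 6.1.1; Protocol 6.1.4). Counting the trial of all four liquids, which starts on Day 1, gives 57 days.
- Follow-up: 14 days, range 12 to 16 (Protocol 6.1.4).

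**1. Check of the day counts against the stated study durations.** The Protocol synopsis gives approximately 14 weeks for myblu and continue-smoking and up to 7 weeks for JUUL.
- Myblu and continue-smoking: 28 screening + 59 on study + 14 = 101 days = 14.4 weeks.
- JUUL: 28 + 3 + 14 = 45 days = 6.4 weeks.

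Both agree.

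**2. Off-supply share of the attribution window** = follow-up days / (use days + follow-up days).
- JUUL: 14/(3 + 14) = 14/17 = 82.4%. Range: 12/15 = 80.0% to 16/19 = 84.2%.
- Myblu from Day 3, the reading that fits the separate Product Trial column: 14/(55 + 14) = 14/69 = 20.3%. Range: 12/67 = 17.9% to 16/71 = 22.5%.
- Myblu from Day 1: 14/(57 + 14) = 14/71 = 19.7%. Range: 12/69 = 17.4% to 16/73 = 21.9%.
- Continue-smoking: 0%, if these subjects keep smoking.

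These are shares of calendar time for a completer (for myblu, one who stays on one liquid). They are not shares of AEs.

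**3. Sensitivity for JUUL.** If the separate Day -2/-1 summary were applied to JUUL as well, its window would be Day 1 plus follow-up: 14/15 = 93.3%. Protocol 6.1.2 defines a Baseline Period only for the other two arms, so 82% is the better reading.

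**4. What the tables would show.** They print subjects with an AE and numbers of AEs, not daily rates. As an illustration only, assume constant rates, an e-cigarette rate half the cigarette rate, and a full return to smoking at discharge. In units of the cigarette rate per day, the expected events per subject are:
- As planned: JUUL 3 × 0.5 + 14 = 15.5; myblu 55 × 0.5 + 14 = 41.5; myblu to JUUL 41.5/15.5 = 2.7.
- On-product time only: JUUL 3 × 0.5 = 1.5; myblu 55 × 0.5 = 27.5; myblu to JUUL 27.5/1.5 = 18.

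The two e-cigarettes are equal by assumption, so both ratios come from unequal days. Restricting to on-product AEs makes the raw-count contrast larger unless exposure time is printed.

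**The case against.** The strongest reply has five parts.

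- **The attribution is partly inferred.** The last-product rule is written for a missing onset time, and Protocol 6.9.2 asks for date and time of onset for every AE, so it should seldom apply. For timed AEs the SAP does not say how a follow-up onset is assigned. A reader might infer that the SAP expressly charges all follow-up AEs to the last e-cigarette; it does not. The inference from the open window, compulsory attribution and the columns on offer still stands, because no other destination is provided.
- **Off supply is not the same as off product.** Self-reporting ends on Day 57. Both e-cigarettes are on the US market, Appendix 9 asks myblu subjects about buying the assigned product, and all subjects receive cessation advice at discharge (Protocol 6.11). Myblu subjects may also smoke during the ambulatory periods without a deviation (Protocol 4.3.3). This stands: neither the return to smoking nor the 0% for cigarettes is established.
- **No numerical bias is shown.** A reader might infer that the e-cigarette columns are pulled towards the cigarette rate by a calculable factor, with JUUL made to look worse than an equal myblu. The documents do not support this. That argument needs daily rates, which the SAP does not tabulate. In counts, step 4 has myblu above JUUL, the opposite direction.
- **Keeping post-use AEs is legitimate**, and no inferential AE comparison is planned. JUUL is a nicotine-uptake comparator in the PK sub-study. This stands and limits the importance.
- **Follow-up AEs can be traced.** The listings give onset date and time, product and relationship, and Table 14.3.1.3 shows relationship. That helps a reader who goes to the listings, but Tables 14.3.1.1 and 14.3.1.2 are not restricted by relationship.

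**Conclusion.** The concern holds as a gap in the attribution rule and the table layout. As written, SAP 7.4 and its shells place AEs arising in the 14 (± 2) days after discharge under the last study product. Off-supply time is 82% of the JUUL window (80% to 84%), about 20% of the myblu window (17% to 23% across both starting days), and 0% for continue-smoking if smoking continues.

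These figures rest on calendar days for completers and on study supply ending at discharge. They do not measure how many AEs are misplaced, and no distortion of a rate or ratio can be claimed from the documents. Since the tables are descriptive, this is a cheap improvement of minor to moderate importance.

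**What to change.** 1. In SAP 7.4, end product attribution at study discharge or early termination plus a short lag whose length is stated.
2. In Tables 14.3.1.1 to 14.3.1.3, show AEs with later onset in a separate Follow-up column split by arm, on the model of Product Trial, and add a total that includes them.
3. Print each product's on-product person-days beside the counts, so that about 3 days per JUUL subject and about 55 per myblu subject are not read as comparable raw counts. Step 4 of the working shows why items 1 and 2 should not be adopted without this.

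The cost is a few sentences in the SAP, extra columns and a row of person-days. No new data are needed. There are two drawbacks. Delayed or withdrawal events move to the follow-up column, where they stay visible. The JUUL on-product column becomes sparse: with 20 subjects planned it covers about 20 × 3 = 60 person-days, against 20 × 14 = 280 in follow-up.

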7.6 Safety

All clinical safety data will be listed by subject and time point and summarized as described in the SAP.

All reported events captured in the database will be listed in by-subject data listings. However, only study product use-emergent AEs. A study product use-emergent AE is defined as an AE that is starting or worsening at the time of or after the first study product use on Day -2.

Frequencies of subjects with study product use-emergent AEs, regardless of relationship to study product will be summarized and sorted by system organ class. Frequencies of subjects

with study product use-emergent SAEs will be likewise summarized. Frequencies of study product use-emergent AEs will be summarized by severity and relationship to study product.

Changes in physical examinations (if any) will be described in the text of the final report.

All prior and concomitant medications recorded during the study will be listed by subject.

The following pre- and post-bronchodilator lung function variables will be summarized.

- Measured and percent of predicted FEV₁
- Measured and percent of predicted FVC
- Measured and percent of predicted FEV₁:FVC ratio
- Measured and percent of predicted FEF_{25-75%}

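### The SAP's rule for adverse events with a missing onset date exempts the wrong group relative to its own definition of product use-emergent

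*SAP*

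**What the plan says.** SAP 7.4 gives the governing definition: "A PUEAE is defined as an AE that is starting or worsening at the time of or after the first randomized study product use". It lists every AE by subject but restricts the tabulations: "only product use-emergent AEs (PUEAEs) will be summarized". Attribution to a product is by timing: "Each PUEAE will be attributed to a study product based on the onset date and time of the AE".

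For undated events the rule has two parts. The default is "If the onset date of an AE is missing, then the AE will be considered product use emergent". The exception is "unless the onset date is known to have occurred within or between specific product use days". Nothing says how an excepted event is classified, or to which product it goes.

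The section also plans a separate summary of AEs from Days -2 and -1, and a listing of serious AEs with no emergence condition.

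Protocol 7.6 uses a different starting point for emergence: "starting or worsening at the time of or after the first study product use on Day -2". SAP 8 nevertheless describes the SAP analyses as aligned with the protocol.

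**The concern.** A missing-date rule for AEs normally counts the event unless there is evidence that it came before exposure. Here the evidence that lifts the default is evidence that the event came during exposure. An AE of wholly unknown timing counts, while one known to have begun between two days of product use is taken out of the default.

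Safety over 56 days of use is a stated secondary objective. The AE frequency tables are restricted to emergent events, so this classification decides which undated events are counted. Undated onsets are plausible in the ambulatory period. Visits fall on Days 14, 28, 42 and 56, which are 14 days apart, and AEs are asked about at scheduled visits. A subject may recall an event only as having happened since the last one. Two programmers working from this text could produce different AE tables.

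**Working it through.** No arithmetic applies. The check sets the missing-date sentence beside the definition in the same section, then follows each kind of event to the planned displays. It takes product use days to mean days of randomized product use, as the SAP definition does.

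**Step 1. Classify each kind of undated AE.**

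| What is known about onset | Missing-date sentence, literally | SAP definition | Result |
|---|---|---|---|
| Nothing | Emergent | Cannot be decided | No conflict; conservative default |
| Before first randomized use | Emergent, because the exception does not reach it | Not emergent, unless it worsened later | Conflict |
| Within or between product use days, after first randomized use | Excepted; no outcome stated | Emergent | Conflict if excepted means not emergent |

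**Step 2. How wide the exception is.** Protocol Table 2 plans product use on every day from Day 1 to Day 57 in the myblu and continue-smoking arms. In those arms the exception spans the whole planned exposure period.

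**Step 3. Where an excepted event goes.** There are two readings.

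- *Excepted means not emergent.* The event is absent from Tables 14.3.1.1, 14.3.1.2 and 14.3.1.3, which the SAP 9 table list titles as product use-emergent. In the myblu and continue-smoking arms the Day -2/-1 summary does not catch it either, because it began later. It stays in the Appendix 16.2.7 listings and, if serious, in Table 14.3.2.1, whose title is not restricted to emergent events.
- *The exception only suspends the default.* The definition then governs, the event is emergent, and it stays in the tables.

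On both readings the second row of the table is unchanged: an undated event known to predate first randomized use is still counted as emergent.

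**Step 4. The anchor.** In the myblu and continue-smoking arms, first randomized use is on Day 1, while Protocol 7.6 starts from Day -2. Events on Days -2 and -1 are therefore emergent under the protocol and not under the SAP. In the JUUL arm the assigned product is used from Day -2, so the two anchors coincide. Protocol 6.9.2 records events before product use on Day -2 as medical history. Under the protocol's anchor, then, almost no recorded AE would be pre-exposure. The third row conflicts under either anchor.

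**Step 5. Size.** The number affected equals the number of AEs with no onset date but a known interval within the use period. Neither document gives an expected AE count or a rate of missing onset dates, so no figure can be computed.

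**The case against.** The strongest reply is that the exception gives no outcome, so it merely lifts a default and hands the event back to the definition, which makes it emergent. The neighbouring sentences support this. They deal with attribution to a product, and the author may have meant that a known interval replaces the default attribution. This reading is plausible, and it makes loss from the tables possible rather than certain. It does not rescue the sentence: the text does not say so, and known pre-exposure events would still be counted.

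The reply is also right that undated events should be few. Protocol 6.9.2 requires date and time of onset, 6.9.1 requires an inquiry at each visit, and 8.3.5 provides edit checks with queries.

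A reader might infer three stronger things that the documents do not support:

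- *That the event vanishes from every AE table.* The serious AE table and the by-subject listings keep it.
- *That the error favours the e-cigarette.* The rule applies to every arm, including continue-smoking, and nothing shows that missing dates differ by arm.
- *That AEs with no clock time have no rule for most of the study.* One missing-time sentence covers the first-use date. The other begins "If onset time of an AE is missing and the onset date does not fall on a study product use date". Neither covers later use days, but on those days the date alone settles emergence. It also settles the product wherever only one is in use, and the AE table shells carry a separate Product Trial column, apparently for the multi-product acclimation days. The real ambiguity is narrow, chiefly Day 29 for subjects who switch e-liquid.

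**Conclusion.** The concern stands as a drafting error in a stated rule. As written, the missing-onset-date sentence points the opposite way from the emergent-AE definition in its own section. It lifts the default for events that the definition includes and keeps the default for the only group that the definition excludes.

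The consequence is conditional. If the exception is programmed as not emergent, true post-exposure AEs can be missing from the three frequency tables, though never from the listings. If it is programmed as a return to the definition, they stay in. The size is unknown and probably small, and no direction between arms can be claimed. The conclusion rests on the SAP's definition being the governing one. If the protocol's Day -2 anchor governs, the exemption of events during use is still wrong, and the pre-exposure half of the problem largely disappears. The rule is worth correcting because the change costs almost nothing and removes a choice that would otherwise fall to the programmer.

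**What to change.** Replace the missing-onset-date sentence in SAP 7.4 with:

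> If the onset date is missing or partial, the AE is a PUEAE unless available information shows that it began before the first randomized product use and did not worsen afterwards. If the onset is known to lie within an interval of use of one product (or the Product Trial period), attribute it to that product or period; if the interval spans a product change, attribute it to the product in use at the start of the interval and flag it.

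Reconcile the first-use anchor between SAP 7.4 and Protocol 7.6. If the difference is intended, record it in SAP 8.

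The missing-time sentences can stay as they are. If they are clarified, a Day 29 event without a clock time should go to the product in use before reselection, with a flag. Protocol Table 7 has product use from 07:00 to 14:00 that day, and selection and dispensing come before discharge at about 18:00. Using the newly chosen product could therefore credit a morning event to an e-liquid not yet dispensed.

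The cost is a few lines of derivation code and possibly a few more AEs in the tables. The change should be made before database lock.
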